### **Mechanisms of Improved Cerebrovascular Function with Aerobic Exercise**

Arterial stiffening and cerebral endothelial dysfunction associated with aging results in decreased basal perfusion and CVR. These changes are known to contribute to age-related declines in both cognitive and motor functions. Our preliminary work demonstrates that age-related vascular dysfunction is diminished in those that report regular engagement in aerobic exercise.

Importantly, the mechanisms behind aerobic exercise and its influence on the peripheral vasculature have been extensively studied and provide strong support for the beneficial

role of exercise in cerebrovascular health and function. Aerobic exercise is associated with less large-artery stiffness and increased arterial compliance and elasticity. Decreased arterial stiffness is a result of functional changes in vascular smooth muscle tone and structural changes to the arterial wall and extracellular matrix components.

This is critical as it supports the concept that aerobic exercise not only prevents arterial stiffness but also reverses any stiffening that occurs with age. Similarly, repeated studies demonstrate that aerobic exercise protects against the development of microvascular endothelial dysfunction. These studies, in both young and older aerobically-trained adults demonstrate greater NO bioavailability as the primary driver of a healthier endothelial profile. Both rodent and human studies support the use of aerobic exercise to lessen oxidative stress as well. Collectively, these systemic changes result in alteration to the vessel formation, which appears to be the mechanism at play for increased perfusion via increased cardiovascular fitness.

In aging, there is increased risk of cerebrovascular dysfunction due to stiffening of the large arteries and impaired endothelial function. These physiological changes result in decreased perfusion and CVR. Much of the research done in the peripheral vasculature and early cross-section work provide evidence that cerebrovascular targets may be adaptable to an aerobic exercise intervention and serves as the guide for our mechanistic framework. A major gap in our understanding of exercise is how the cerebrovasculature responds to improved cardiovascular fitness in sedentary older adults. We have established an effective exercise intervention that has improved both motor and cognitive function with a concurrent and correlated change in BOLD signal during related tasks. These robust changes are hypothesized to be due, in part, to improved vascular function. As a next step, we propose to examine changes in cortical perfusion as well as changes in CVR following a proven aerobic exercise intervention.

#### **4. Specific Aims:**

The study will enroll 134 older, sedentary adults. Participants will be pseudorandomized to one of two 12-week intervention conditions: Aerobic Exercise or Stretching.

**Specific Aim 1:** To determine the effect of a 12-week aerobic exercise intervention on changes in cerebral perfusion using arterial spin labeling in older Veterans.

*Hypothesis:* Compared to a non-aerobic intervention Control group, the aerobically trained group will have increased basal perfusion in areas that demonstrate age-related decline and are malleable to aerobic exercise (inferior frontal and motor cortices).

**Specific Aim 2:** To determine the effect of a 12-week aerobic exercise intervention on changes in cerebrovascular reactivity using a hypercapnic CO2 response test in older Veterans.

*Hypothesis:* Following the interventions, aerobically-trained older adults will have increased CVR to CO2 in the inferior frontal and motor cortices when compared to controls.

**Specific Aim 3:** To quantify the impact of cerebrovascular perfusion and cerebrovascular reactivity on the BOLD response during task-based (cognitive executive and motor) fMRI.

*Hypothesis:* Perfusion and CVR will account for a significant portion of variability in the BOLD response during task-based fMRI both before and after the intervention.

*Measures for Specific Aim 3.*

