### **Crystallized Word Knowledge**

1. *American National Adult Reading Test (ANART)*: reading test used to help assess intelligence.

All cognitive testing will take place in the primary laboratory of the PI at the Atlanta VA Medical Center. All evaluations will be done by the PI or appropriate study staff. Additionally, to evaluate efficacy of interventions participants will self-report on:

1. Mac-Q- 6 item questionnaire to asking participants to describe their ability to perform memory task as compared to when they were in high school.
2. Behavior Rating Inventory of Executive Function (BRIEF)- Assesses self reported impairment of executive function task related to activities of daily living.
3. Self-Efficacy for exercise scale - a 13-item instrument that measures self-efficacy barriers to exercise,
4. Epworth Sleepiness Scale- self report used to determine the level of daytime sleepiness.
5. Apathy Index (MAI)- 14 item self-report instrument that measures overall apathy and participants interest in new things.
6. Pittsburgh Sleep Quality Index- 10 item questionnaire examining participants sleep habits over the past month.
7. Patient Health Questionnaire (PHQ-9) – 9-item instrument that screens for signs and symptoms of depression.
8. Pelvic Floor Distress Inventory Questionnaire (PFDI-20) – 20 item questionnaire that screens for bowel, bladder, or pelvic symptoms.

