#### **Interventions**

*Aerobic Exercise Group:* For this arm of intervention, randomized participants will attend spin exercise training sessions demonstrated to facilitate physiological changes. For the

aerobic exercise component of this group, participants will follow the guidelines provided by the American College of Sports Medicine for optimizing cardiovascular fitness. Thus, participants will exercise 3 times a week on a stationary ergometer. Exercise intensity will begin at low levels (50% of maximal heart rate reserve) calculated utilizing the Karvonen method. Briefly, target exercise HR is calculated by subtracting the persons age from 220. Resting heart rate is then subtracted from this number. The answer is then multiplied by the target percent (50% for example) and the product is added back to resting heart rate to provide the target exercise session heart rate. Intensity will be increased by 5% every week (as tolerated by the participant) to a maximum of 90% of maximal heart rate. Exercise time will progress from an initial 25 minutes per session to a maximum of 60 minutes by increasing 5 minutes each week. Each session will be monitored by a certified CPR and fitness specialist. Further, the intervention site is located in the Atlanta VA Health Care System and portable defibrillators are available at the intervention site.

*Interval Exercise Group:* For 12-weeks participants will engage in progressive whole body stretching, toning and balance exercises designed for individuals 65 years and older. Participants will meet for the same total duration time as the aerobic exercise group. Heart rate will be monitored to ensure participants maintain exercise levels below aerobic training zone.

*Remote Exercise Monitoring:* As an alternative, participants that are uncomfortable with receiving face-to-face training within the hospital will be given the option to continue their exercise intervention visits remotely. For participants that have been randomly assigned to the 'spin' exercise training program, will be provided a stationary cycle ergometer that has been sanitized properly to use during the 12-week period. All subjects will be monitored and trained through VA and Emory approved remote access sites.

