*Control Group:* A random subset of participants will be in a 12-week wait-list control. These participants will undergo the same scanning procedures as described above without cognitive or physical function testing. After 12-weeks these participants will come in and undergo the pre-assessment, 12-week exercise intervention and post assessment as described above.

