## **6. Participant selection:**

The study will enroll sedentary older adults and young adults as a comparison group for the MRI scans. Older adult participants will be pseudo-randomized to one of three 12week intervention conditions: Aerobic Exercise, Interval Exercise, or Control. The pre and post evaluations will be conducted over 2 days during a 1-week period. Each day will last no more than 2 hours. The investigators expect a dropout rate of anywhere from 15-20% of participants. To ensure completion of study by 108 participants, as many as 134 subjects may be enrolled.

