### **Recruitment**

Individuals will be recruited from the Atlanta VA Rehab R&D Subject Registry (IRB00000159) based on the inclusion and exclusion criteria. The Subject Registry study staff will query the database of all patients meeting the inclusion and exclusion criteria who have consented to be contacted for research purposes and will print out their contact information. The Principal Investigator, or his research colleagues, will contact these individuals and will summarize the study procedures. If the potential participant is interested, we will mail them a copy of the informed consent and will

schedule an orientation session that describes the study goals and provides an opportunity to go over the informed consent.

In order to decrease burden of the potential recruitment pool of participants, cognitive, motor, and physical function measurements will be shared between this study Effects of Acute Exercise on Functional Magnetic Resonance Spectroscopy Measures of GABA in Aging and Chronic Stroke (IRB00001334) and Graded Intensity Aerobic Exercise to Improve Cerebrovascular Function and Performance in Aged Veterans (IRB00106626) as all studies administer the same assessments.

Healthy subjects will also be recruited via the Emory University Alzheimer Disease Research Center (ADRC) Registry. Written permission from all patients is recorded on a signed informed consent form before inclusion in the ADRC Registry. This consent requires that the patients be willing to complete detailed histories, undergo comprehensive neurological and neuropsychological evaluations on an annual basis; submit blood for ascertainment of genetic information and establishment of lymphoblastoid cell lines; and agree to be contacted regarding participation in research projects of Emory investigators.

CDW/VINCI data will be used to identify potential research participants. Veterans who are age 65 or older and who live within 20 miles of the Atlanta VA Health Care System will be identified and contacted via mail and then subsequently by phone. Addresses and phone numbers will be used for recruitment only and the information will be verified as current and accurate in CPRS prior to use.

Additionally, participants may be recruited from word of mouth, newspaper advertisement, and study flyer distribution within the Atlanta VA Health Care System and surrounding community.

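### Allocation is called pseudorandomized but never defined, and nothing requires concealment or release only after baseline, so the causal between-group reading of Aims 1 and 2 is not protected

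*Combined protocol and SAP*

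**What the plan says.** Two places in the combined protocol and SAP define how older adults reach an arm, and both use the prefix pseudo:

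- Section 4, Specific Aims: "Participants will be pseudorandomized to one of two 12-week intervention conditions: Aerobic Exercise or Stretching".
- Section 6, Participant selection: "Older adult participants will be pseudo-randomized to one of three 12week intervention conditions: Aerobic Exercise, Interval Exercise, or Control".

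The Interventions text in section 5 uses the language of ordinary randomization:

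- Aerobic arm: "For this arm of intervention, randomized participants will attend spin exercise training sessions".
- Remote option: "For participants that have been randomly assigned to the 'spin' exercise training program".
- Wait-list: "A random subset of participants will be in a 12-week wait-list control".

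The wait-list group has the initial scans but no cognitive or physical function tests at that point. Section 7 tests Aims 1 and 2 by a mixed model comparing Spin with Control. Gender, race, age, hypertensive status and MoCA score enter only in additional regressions.

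The text available for review gives no method of sequence generation, ratio, blocks or strata. It also names no holder of the sequence, and contains no concealment step and no rule on when the arm becomes known relative to baseline.

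**The concern.** Aims 1 and 2 claim that aerobic training changes perfusion and CVR. That claim needs groups that differ at the start only by chance. As worded, alternation, filling classes in order of arrival, and a concealed computer list would all count as following the plan. Under the first two, whoever enrols can foresee the next arm and can, without bad intent, time or place candidates accordingly. Group exercise classes (Exercise Lab Space) give an ordinary logistic reason to do so.

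The factor most likely to be visible to staff is also relevant to the outcome. The Background reports that people with higher cardiovascular fitness have better CVR. Fitness is not among the factors named for the additional regressions of Aims 1 and 2, and those regressions sit outside the main model in any case. Analysis after the fact would not repair a steered allocation.

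**Working it through.** **1. Is the method defined?** Set side by side, sections 4 and 6 give one undefined term and two different numbers of conditions. The Interventions text gives three phrases that imply chance but no procedure. No list can be built until it is settled whether there are two arms, three arms, or two arms plus a wait-list subset.

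**2. Does anything force allocation to follow baseline?** Consent before study procedures (consent process) and written medical approval before any part of the study (Inclusion/Exclusion Criteria) are required. Completion of the baseline scan and tests before the arm is known is not. For the wait-list the plan implies the reverse. These participants skip the initial cognitive and physical tests, so staff must know who is wait-listed before those tests would be done.

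**3. The plan's own between-group figure.** Power Analysis and Sample Size gives 44 per group, d=0.64 and power 0.80 for semantic fluency. At two-sided alpha 0.0261 (the FDR-corrected level used elsewhere in that section), the normal approximation gives 0.78 and the noncentral t gives 0.77, close to the stated value. At 0.05 the normal approximation gives 0.85. The d=0.64 is therefore usable as a two-group yardstick. No between-group figure is given for perfusion or CVR.

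**4. Illustrative bias.** Suppose a fraction p of each arm is exchanged for people whose expected change differs by δ SD. Both p and δ are assumptions; δ=1 throughout.

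- Difference expressed only in Spin: bias = p × δ.
- Difference expressed in both arms: bias = 2 × p × δ.

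| p | Spin only | Share of 0.64 | Both arms | Share of 0.64 |
|---|---|---|---|---|
| 5% | 0.05 SD | 0.05/0.64 = 8% | 0.10 SD | 0.10/0.64 = 16% |
| 10% | 0.10 SD | 0.10/0.64 = 16% | 0.20 SD | 0.20/0.64 = 31% |

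**5. Effect on false positives.** With 44 per group, no true effect and a two-sided two-sample t test (noncentrality = bias × √(44/2)):

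| Bias | Rate at nominal 0.0261 | Rate at nominal 0.05 |
|---|---|---|
| 0.1 SD | 0.043 | 0.075 |
| 0.2 SD | 0.098 | 0.153 |

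**6. Why d=0.5 is not the yardstick.** The plan derives d=0.5 for change within the Spin group (n=44). At two-sided alpha 0.0261 a one-sample test has power 0.84 at d=0.5, while a two-group test with 44 per arm has only 0.53. A between-group bias should not be expressed as a share of it.

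**The case against.** The strongest reply is that the gap may be one of description only. FMRI Tasks uses the same prefix for trial order: five runs of 14 trials yield exactly 35 memory and 35 control trials, which is constrained but random ordering. On that usage, pseudorandomized arms could mean blocked or stratified randomization, in agreement with the Interventions text. This stands. A conflict over whether allocation is random is possible, not established.

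A reader might go further and infer that an unmasked team allocates openly, without a list, and that the same people recruit, consent, test and train. The documents do not support this. Recruitment says "The Principal Investigator, or his research colleagues, will contact these individuals and will summarize the study procedures", and the cognitive testing text says "All evaluations will be done by the PI or appropriate study staff". Elsewhere there are registry staff, trained consenting staff, a certified examiner, a nurse or exercise physiologist, and a fitness specialist. Overlap is possible but not stated, and silence on masking or on a list does not show that either is absent. Nor does any section tie class capacity, fitness or preference to placement, and the remote option loosens any capacity limit.

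Two limits on size also stand. Controls are kept below the aerobic training zone or wait-listed, so a difference in capacity to respond to training would show mainly in Spin; that favours the lower figure. And early knowledge of the arm could alter effort on fitness or cognitive pre-tests, but resting perfusion and the CO2 response depend little on effort.

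None of this supplies a concealment step or a release rule.

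**Conclusion.** The point holds as a weakness of the stated method. Allocation is named by an undefined term in both defining places and described as random elsewhere. No available text requires concealment or release after baseline. Predictable or steered assignment is therefore permitted by the wording, and the causal comparison in Aims 1 and 2 is unprotected. It is not shown that any steering occurs.

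The size is an illustration only: 0.1 to 0.2 SD, or about 16% to 31% of d=0.64, on an assumed 10% exchange and an assumed 1 SD difference, against a yardstick stated for semantic fluency rather than perfusion or CVR. The conclusion about procedure does not depend on these numbers. Some front matter was removed before review, so absence is judged on the remaining text.

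**What to change.** 1. Reconcile the descriptions first: two conditions in section 4, three in section 6, and the wait-list subset under Interventions. State the ratio.

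2. In sections 4 and 6, replace pseudorandomized with a computer-generated random list, for example permuted blocks of varying size. An existing team member who neither enrols nor tests should prepare it. It should cover every arm, including any wait-list, and be concealed from those who enrol.

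3. Release one assignment at a time, after consent, medical clearance and the baseline scan, and after the baseline tests for arms that have them. If the wait-list stays, a two-step release would work: wait-list or immediate start after the scan, then type of exercise after the tests. This needs the scan to come before the tests.

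4. REDCap could hold the list if its allocation function is set up; the plan describes it only for data entry and analysis.

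5. If assignments already made were not random, say so and describe the trial as non-randomised. If a sound method is already in use, describing it closes the point.

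Cost: a few sentences of protocol text and a one-time list set-up. Sample size, power and number of visits do not change. The downside is less freedom to fill exercise classes.

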## **5. Design and Methods:**

### **Video and Telephone Consent Process**

To limit face-to-face interactions with participants, the study will be using Emory and VA approved video or audio communication to screen and consent. Some VA-approved virtual methods include Microsoft Teams Version 1.3+, Zoom 5.0 or greater, and Cisco WebEx version 40+. Recordings of the audio or visual communication will not be permitted. If the participant meets initial eligibility criteria, we will mail or email through VA Outlook using encryption two unsigned copies of the ICF/HIPAA. We will ensure the individual has enough time after receiving the document to read it before scheduled phone/video call. Trained staff will perform consenting process including speaking with the individual to discuss the study and highlighting each section of the consent form, allowing the participant an opportunity to ask questions before providing consent, and giving the participant enough time to consider being in the study. Study team will inform the individual that if they would like to take more time to consider the study, another telephone call can be scheduled. If the individual would like to participate, the participant will sign and date the document and return it to study team via mail or via email to the VA Outlook email address. If the participant chooses to return the signed consent via email, they are required to send the consent as a reply to the original VA encrypted message sent by study staff. The study team will write a "Note to File" documenting everything about the interaction including:

1. When and how the consent form was sent
2. When the video/telephone call was made
3. What was discussed during the call
4. When the signed consent form was received
5. When the signed consent form was signed by the person obtaining consent
6. When a copy of the consent form signed by both subject and study team was given to the participant
7. A description of why signature dates are different (if applicable)

Once the study team receives the signed consent form, the person obtaining consent should sign the form and date it for the day it was signed. Study procedures will begin

once the signed copy is received. A copy of the fully signed consent form will be given to the participant via mail or in person at the next scheduled visit.

If consent is virtual, the option for DocuSign will be offered to the potential participant. A DocuSign envelope (email containing the links to study documents) with a reminder to NOT sign the documents prior to the scheduled contact time to review the documents with study staff and have questions answered. At the scheduled time the study team member consenting will contact the potential participant via VA and Emory-approved video or audio communication to guide the patient through the opening the DocuSign envelope and will review the documents contained.

As per standard review of consent, the study team member will review the study consent. Trained staff will perform consenting process including speaking with the individual to discuss the study and highlighting each section of the consent form, allowing the participant an opportunity to ask questions before providing consent, and giving the participant enough time to consider being in the study. Study team will inform the individual that if they would like to take more time to consider the study, another telephone call can be scheduled. If the individual would like to participate, the study team member will guide the participant through completion of the fields in the study documents to sign them and finalize the documents. The study team member will then receive an email from DocuSign while still in the consent session with the participant and will verify it is completed correctly and accurately. The study team member will then guide the participant through downloading a copy of the signed consent documents to their local computer for their records. Thank them and conclude the call. The study team member will download a signed copy to the study folder on the VA network drive as the study record and a copy will be provided to Health Information Systems for upload to the medical record. The study team will document the consenting process in a "Research Consent Progress Note" in the VA medical record (CPRS or new system when we transition) everything about the interaction including:

1. When and how the consent form was sent
2. When the video/telephone call was made
3. What was discussed during the call
4. When consent was reviewed virtually and signed via DocuSign with a copy downloaded to their local computer for their records.

Study procedures can begin once the DocuSign copy is received and documented

